4.5 Interim Analysis for Effectiveness

Not applicable.

5 SAFETY ANALYSIS STRATEGY

5.1 Safety Endpoints

The safety endpoints are:

- Ocular and nonocular AEs and SAEs
- Device deficiencies
- Secondary surgical interventions
- Unplanned intraoperative procedures

5.2 Safety Hypotheses

There are no formal safety hypotheses in this study. The focus of the safety analysis will be a comprehensive descriptive assessment of safety endpoints listed in Section 5.1.

5.3 Statistical Methods for Safety Analyses

All adverse events occurring from the time a subject sign informed consent to study exit will be accounted for in the reporting. Safety analyses will be conducted using the safety analysis set on a treatment-emergent basis. Descriptive summaries (counts and percentages) and listings will be presented. Individual subject listings will be provided for AEs that occur after signing informed consent but prior to exposure to IP.

5.3.1 Ocular and Nonocular AEs and SAEs

All adverse events reported to Alcon will be accounted for in the reporting. Descriptive summaries (counts and percentages) and listings will be presented. The type of event (serious, device related, etc.) will be summarized overall and by ocular/non-ocular status. Events will also be summarized by MedDRA preferred term, with the number and percent of subjects and a 95% exact binomial confidence interval, as well as a count of the number of events. The applicable definition of an adverse event is in the study protocol. A listing of all adverse events will be constructed to provide further details.

5.3.2 Device Deficiencies

The applicable definition of a device deficiency is in the study protocol. A frequency table showing counts for each device deficiency category will be presented. In addition, a listing of all device deficiencies will be provided.

5.3.3 Secondary Surgical Interventions

Descriptive statistics (counts, percentages, and two-sided 95% exact binomial confidence intervals) of eyes with secondary surgical interventions (SSIs) will be presented. In addition, a listing of subjects with SSIs will be produced.

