### **7.3 Rationale for Duration of Treatment/Follow-up**

The follow-up schedule was designed to allow collection of data at key time points that yield relevant performance and safety outcomes. The follow-up period will allow for adequate safety monitoring of adverse events; if patients develop complications, those will typically be present within approximately 1 month of cataract surgery and 3-months of vitreoretinal surgery.

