## **8 STUDY POPULATION**

The study population will consist of male and female subjects (18 years or older) requiring posterior segment surgery in the operating room with or without simultaneous cataract surgery (unilaterally). It is aimed to enroll (consent) approximately 120 subjects in up to 8 sites in AUS and/or the USA with a target of 100 subjects treated, with approximately 10 to 40 subjects per

site. Site-specific targets may vary based upon individual site capabilities and each site may include more than one surgeon. Estimated time needed to recruit subjects for the study is approximately 3 months; however, unanticipated circumstances may shorten or lengthen this time and would not require amendment of this protocol. Because a 10% screening failure rate is expected and 10% for loss to follow-up, approximately 120 subjects are expected to be enrolled to ensure 100 completed subjects.

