## 10 STUDY PROCEDURES AND ASSESSMENTS

Study assessments will be obtained prior to vitreoretinal with or without simultaneous cataract surgery with the UNITY VCS and postoperatively at the study visits outlined below:

- Screening – Visit 0 (Day -30 to 0 prior to treatment)
- Surgery – Visit 00 (Day 0)
- 1 Day – Visit 1 (Day 1 to 3)
- 1 Week – Visit 2 (Day 4 to 10)
- 1 Month – Visit 3 (Day 16 to 44)
- 3 Month/Exit – Visit 4 (Day 76 to 104)

In addition to the scheduled visits listed above, the following visit may apply as needed:

- USV (completed when a treated subject reports for additional follow-up)
- Early Termination Visit (when subject would like to withdraw from the study participation)

Clinical assessments to be obtained at study visits are outlined in [Table 3-1](#) Schedule of Study Procedures and Assessments and are defined in the sections below.

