2.2 Safety Analysis Set

The safety analysis set will include all eyes with attempted use of the UNITY VCS (successful or aborted after contact with the eye) and will be used for the safety outcomes. Attempted use of the UNITY VCS is defined as any time the device makes contact with the eye.

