7 SAMPLE SIZE AND POWER CALCULATIONS

Based on a sample of 100 surgeries, the expected half-width of the 95% confidence interval for the percentage of surgeons reporting 'yes' to the question "***Did UNITY VCS using vitreoretinal or combined surgical functionality perform per the intended use as defined in protocol Section 5.1?***" will be $1.96\sqrt{p(1-p)/100}$. This half-width is widest at $p = 50\%$. Under this conservative assumption, the expected half-width is < 10% given the sample size of 100.

Allow enrollment for an additional 10% for screen failure and 10% for loss to follow-up to ensure 100 completed subjects.

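### The secondary surgical intervention percentage makes no allowance for eyes lost before 3 months, so as an estimate of 3-month risk, loss can only bias it downwards

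*SAP*

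**What the plan says.** SAP 5.3.3 defines the SSI summary as follows: "Descriptive statistics (counts, percentages, and two-sided 95% exact binomial confidence intervals) of eyes with secondary surgical interventions (SSIs) will be presented". A listing goes with it, and Protocol 12.6.1 says the same. The denominator comes from SAP 5.3 ("Safety analyses will be conducted using the safety analysis set on a treatment-emergent basis") and SAP 2.2 ("The safety analysis set will include all eyes with attempted use of the UNITY VCS (successful or aborted after contact with the eye"). Any eye the device touched is in, however long it was followed.

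The plan expects incomplete follow-up. SAP 7 says: "Allow enrollment for an additional 10% for screen failure and 10% for loss to follow-up to ensure 100 completed subjects". Protocol 8 adds that "approximately 120 subjects are expected to be enrolled to ensure 100 completed subjects".

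Protocol 7.3 ties the length of follow-up to the period in which complications appear: "if patients develop complications, those will typically be present within approximately 1 month of cataract surgery and 3-months of vitreoretinal surgery". Protocol 12.5 plans no imputation. In the public text, neither document gives the SSI percentage a time point, a censoring rule, a denominator based on follow-up or a sensitivity analysis.

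**The concern.** An eye that leaves the study early stays in the denominator, but an SSI after it leaves is likely to go unseen. Observed SSIs are a subset of all SSIs. Dividing them by all treated eyes therefore cannot give more than the true 3-month proportion in those eyes, and gives less whenever a lost eye has a later SSI that nobody records. The error favours the device.

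SSI is one of four listed safety endpoints (SAP 5.1). Protocol 7.2 defends the single-arm design on the ground that the safety results can be set against published evidence. That comparison needs a rate with a stated horizon and known follow-up. The exact binomial interval reflects sampling error only, so it gives the reader no sign of what loss might hide.

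**Working it through.** **Inputs.** From SAP 7 and Protocol 8: about 120 enrolled, 100 completed, an additional 10% for screen failure and 10% for loss. Assumed here, because the documents give no SSI rate: a true 3-month risk *p* of 2% to 20% and, where timing matters, a constant hazard over 90 days.

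**The plan's own figures.**
- Enrolment: 100 + 10 + 10 = 120, which reproduces the stated number. Taking off the 10 screen failures leaves 110 treated, of whom 100 complete. The share lost is 10/110 = 9.1%.
- Precision, stated for the primary endpoint only: 1.96 × √(0.5 × 0.5/100) = 9.8 points, which reproduces the stated bound of under 10%.
- No expected figure is stated for SSIs.

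**Loss unrelated to SSI risk.**
- All 10 eyes lost at once (the largest shortfall): reported rate = *p* × 100/110.
- Losses spread evenly over 90 days: a lost eye shows its SSI before leaving with average probability *m* = 1 − *p*/(−ln(1 − *p*)), and the reported rate = (100*p* + 10*m*)/110. At *p* = 10%, *m* = 1 − 0.1/0.10536 = 0.0509, giving (10 + 0.509)/110 = 9.55%.

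| True 3-month risk (assumed) | Reported, all losses immediate | Reported, losses evenly spread |
|---|---|---|
| 2% | 1.8% | 1.9% |
| 5% | 4.5% | 4.8% |
| 10% | 9.1% | 9.55% |
| 20% | 18.2% | 19.1% |

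If SSIs come early (assumed mean 20 days) and losses are evenly spread, 10% reads 9.8%. For scale, the exact 95% interval for 10/110 is 4.5% to 16.1%.

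**Loss related to SSI risk.** Completers are held at 10%, so they contribute 10 SSIs.
- Lost eyes at 20% risk, lost at once: truth (10 + 2)/110 = 10.9%; reported 10/110 = 9.1%.
- Lost eyes at 50% risk: truth (10 + 5)/110 = 13.6%. With immediate loss the report shows 10/110 = 9.1%. With even loss, *m* = 1 − 0.5/ln 2 = 0.279 and the report shows (10 + 2.79)/110 = 11.6%.
- Extreme bound, every lost eye having an unseen SSI: truth 20/110 = 18.2%; reported 9.1%. This bound lies above the upper limit of the reported interval (16.1%).

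**What Kaplan-Meier would do.** If loss is unrelated to risk it targets the true *p*. In the case of 50% risk and immediate loss it returns about 10/100 = 10%, against a truth of 13.6%. It removes the first kind of bias, not the second.

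**The case against.** The plan never calls the percentage a 3-month risk, and as the observed incidence among treated eyes it is correct. This is a feasibility study with no hypothesis test. Disposition summaries (SAP 3) and an SSI listing are already planned. The documents do not say how the external rates were calculated, so a Kaplan-Meier figure may or may not match them better. Nothing in the documents says that loss is related to SSI. All of this stands. It limits the point to a minor one but does not remove it, because Protocol 7.2 and 7.3 give the reader every reason to take the percentage as a 3-month figure.

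Two stronger readings are tempting, and the documents support neither.

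- **A reader might infer that every lost eye is counted as SSI-free for 3 months.** SSI information is collected at unscheduled visits (Protocol 10.3). SSIs, apart from listed exclusions, are reportable as serious adverse events (Protocol 11.1) and documented within 24 hours of awareness (Protocol 11.3). Discontinuing subjects complete exit procedures where willing and able (Protocol 10.4.2). Only the unobserved time after loss is affected. Care given elsewhere is recorded once the investigator becomes aware of it (Protocol 10.3), so an SSI performed elsewhere could be missed, but it need not be.
- **A reader might infer that the exit window, "Visit 4 (Day 76 to 104" in Protocol 10, adds to the downward bias.** The window is symmetric about Day 90. With a constant hazard giving 10% at Day 90, cumulative risk is 1 − 0.9^(76/90) = 8.5% at Day 76 and 1 − 0.9^(104/90) = 11.5% at Day 104. Early and late exits roughly cancel.

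**Conclusion.** The point holds, and it is minor. The SSI percentage is crude, and as an estimate of 3-month risk, loss to follow-up can bias it only downwards. If loss is unrelated to SSI, the shortfall is at most about 9% in relative terms (a factor of 100/110), or under 1 point at an assumed 10% risk. Sampling error is far larger. The shortfall is material only if lost eyes carry a much higher risk, and its size then depends heavily on when they are lost: at an assumed 50% risk, about 4.5 points with immediate loss (13.6 − 9.1) and about 2 points with even loss (13.6 − 11.6).

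These sizes rest on the additive reading of the enrolment figures, the assumed SSI rates and, for even loss, a constant hazard. Protocol 8 also mentions a target of 100 treated. If 10 of 100 treated eyes were lost, the factor would be 90/100 and a true 10% would read 9.0% at worst, so the conclusion does not change. The direction of the bias needs none of these assumptions.

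**What to change.** In SAP 5.3.3, keep the crude count, percentage and exact interval, and add three items:

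1. The number of safety-set eyes followed to at least Day 76, the opening of the 3-month visit window.
2. The Kaplan-Meier cumulative incidence of SSI at Day 90 with a 95% confidence interval, using the same SSI definition as the crude count and censoring at last contact.
3. One worst-case line that counts every lost eye without a recorded SSI as having had one. This is needed because Kaplan-Meier assumes that loss is unrelated to risk. Label it as a bound, not an estimate.

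The same treatment of retinal detachment is optional, as it is not a separate endpoint.

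The cost is one extra table and a slightly less favourable rate. No new data are needed: serious adverse event documentation includes the date of occurrence (Protocol 11.3), and visit and study completion dates are source data (Protocol 13.2).

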5.3.4 Unplanned Intraoperative Procedures

Unplanned intraoperative procedures that occur during surgery will be recorded. Descriptive statistics including the count, percentage, and a two-sided 95% exact binomial confidence interval for the percentage will be produced and will be accompanied by a listing.

5.3.5 Additional Safety Analysis

5.3.5.1 Biomicroscopy Findings/Slit Lamp Examination

A slit-lamp examination will be performed at the screening, 1 day, 1 week, 1 month, and 3 month visits to evaluate the anterior segment of the eye, including eyelids/conjunctiva, cornea, lens, and iris/anterior chamber. A summary of grading at each visit for corneal edema, aqueous cells, and aqueous flare will be presented. Cataract grading and cataract type will be presented for the screening visit. A listing with this information, plus details on any abnormal slit lamp findings, will be provided. Additionally, a listing of postoperative IOL observations will be created.

[figure not shown]
5.3.5.2 Intraocular Pressure

Intraocular pressure (IOP) measurements will be recorded in mmHg and rounded to the nearest whole mmHg. IOP measurements will be conducted at the screening, 1 day, 1 week, 1 month, and 3 month visits.

Descriptive summaries (count, mean, median, standard deviation, minimum and maximum) of observed values will be presented at each study visit and for the change at 1 day, 1 month and 3 months from baseline. A listing will supplement the summary table.

5.3.5.3 Dilated Fundus Examination

The dilated fundus examination will be conducted at the screening, 1 week, 1 month and 3 month visits. The dilated fundus examination may also be conducted at the 1 day visit as needed. The examination will be performed to evaluate the health of the vitreous, retina including peripheral retina, macula, choroid, and optic nerve. A listing of fundus findings will delineate the results.

7 SAMPLE SIZE AND POWER CALCULATIONS

Based on a sample of 100 surgeries, the expected half-width of the 95% confidence interval for the percentage of surgeons reporting 'yes' to the question "***Did UNITY VCS using vitreoretinal or combined surgical functionality perform per the intended use as defined in protocol Section 5.1?***" will be $1.96\sqrt{p(1-p)/100}$. This half-width is widest at $p = 50\%$. Under this conservative assumption, the expected half-width is < 10% given the sample size of 100.

Allow enrollment for an additional 10% for screen failure and 10% for loss to follow-up to ensure 100 completed subjects.

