Data analysis and sample size justification	
The primary analysis set for effectiveness outcomes will be the full analysis set. The full analysis set includes all eyes with successful completion of surgery. The safety analysis set will include all eyes with attempted use of the UNITY VCS (successful or aborted after contact with the eye) and will be used for the safety outcomes. Attempted use of the UNITY VCS is defined as any time the device makes contact with the eye.
 
There will be no hypothesis testing for any study outcome. All study outcomes will be presented as data listings or with summary statistics that are appropriate to the scale of the endpoint (continuous, dichotomous, etc.).
 
Based on a sample of 100 surgeries, the expected half-width of the 95% confidence interval for the percentage of surgeons reporting 'yes' to the question "Did UNITY VCS using vitreoretinal or combined surgical functionality perform per the intended use as defined in protocol Section 5.1?" will be <math>1.96\sqrt{p(1-p)/100}</math>. This half-width is widest at <math>p = 50\%</math>. Under this conservative assumption, the expected half-width is <math>< 10\%</math> given the sample size of 100.
 
Allow enrolment for an additional 10% for screen failure and 10% for loss to follow-up to ensure 100 completed subjects.

--	---

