## 4 PROTOCOL AMENDMENTS

Modification of the protocol is prohibited without prior written agreement in the form of a protocol amendment. All amendments must be created by the study sponsor and must be approved by the IRB/IEC and global and regional health authorities, as applicable, prior to implementation except when required to mitigate immediate safety risks or when the changes involve only logistical or administrative revisions.

Amendments may necessitate that the informed consent and other study-related material be revised. If the consent form is revised, all subjects currently enrolled in the study must sign the approved, revised informed consent (re-consent), as required by the IRB/IEC.

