#### 12.4.1.2 Analysis Methods

After each surgery, the surgeon completes a user questionnaire. For subjects in the full analysis set, the rate of 'yes' responses to the question listed above will be presented with a count and percentage and will be accompanied by a two-sided exact binomial 95% confidence interval.

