4.2 Effectiveness Hypotheses

No hypothesis testing will be performed. Analyses will be descriptive only.

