4.3.1 Analysis of the Primary Endpoint

After each surgery, the surgeon completes a user questionnaire. For subjects in the full analysis set, the rate of ‘yes’ responses to the question ***“Did UNITY VCS using vitreoretinal or combined surgical functionality perform per the intended use as defined in protocol Section 5.1?”*** will be presented with a count and percentage and will be accompanied by a two-sided exact binomial 95% confidence interval.

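### The precision claimed for 100 surgeries (half-width below 10% at p = 50%) holds for the printed normal-approximation formula (9.8%) but not for the exact binomial interval to be reported (10.2 points)

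*SAP*

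**What the plan says.** The sample size justification appears in SAP section 7, Protocol 12.8 and the data analysis row of the Protocol section 3 summary. The SAP version opens: "Based on a sample of 100 surgeries, the expected half-width of the 95% confidence interval for the percentage of surgeons reporting" yes to the intended-use question. It sets this half-width equal to 1.96·√(p(1−p)/100), takes p = 50% as the widest case, and concludes: "Under this conservative assumption, the expected half-width is < 10% given the sample size of 100". The two Protocol passages give the same formula and the same bound.

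The analysis sections name a different interval for the same endpoint. Under SAP 4.3.1 the rate of yes responses "will be accompanied by a two-sided exact binomial 95% confidence interval". Protocol 12.4.1.2 likewise asks for a "count and percentage and will be accompanied by a two-sided exact binomial 95% confidence interval".

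SAP 4.2 sets the inferential context: "No hypothesis testing will be performed. Analyses will be descriptive only".

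**The concern.** The precision statement describes a normal-approximation (Wald) interval, while the study report will contain an exact binomial interval. Exact intervals are generally wider, and the printed formula clears the 10% mark by only 0.2 points at p = 50%. A strict bound with so little room may not survive the change of method.

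This sentence is the plan's only quantitative reason for choosing 100 surgeries. If the planned interval does not meet the bound, a reader comparing the report with the plan will find that the promised worst-case precision was never available at that sample size. With no hypothesis test and no success threshold, what is at stake is the accuracy of the stated justification, not any conclusion about the device.

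**Working it through.** **Inputs**
- n = 100 surgeries, p = 50%, half-width 1.96·√(p(1−p)/100), stated bound < 10%: SAP section 7, Protocol 12.8, Protocol section 3 summary.
- Interval to be reported: two-sided, 95%, exact binomial: SAP 4.3.1, Protocol 12.4.1.2.
- Assumption: exact means the equal-tailed Clopper-Pearson interval. The documents do not name the variant.

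**Step 1. Reproduce the plan's figure.** 1.96·√(0.5 × 0.5/100) = 1.96 × 0.05 = 0.0980, or 9.80 points. This is below 10, so the printed arithmetic is right for the printed formula.

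**Step 2. Exact interval at 50/100.** For x yes responses out of n, the lower limit is the 2.5% quantile of Beta(x, n − x + 1) and the upper limit is the 97.5% quantile of Beta(x + 1, n − x). With x = 50 and n = 100:
- lower limit 0.3983, upper limit 0.6017
- half-width (0.6017 − 0.3983)/2 = 0.1017, or 10.17 points

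This is the largest half-width over all outcomes from 0 to 100, so 50% is the widest case for the exact interval too.

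**Step 3. Expected in the sense of an average.** Averaging the exact half-width over X ~ Binomial(100, 0.5) gives 0.1012, or 10.12 points. The bound fails whether expected means the value at 50/100 or the mean.

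**Step 4. Where the bound fails at n = 100.**
- By observed count: the exact half-width is 10 points or more for 41 to 59 yes responses (10.01 at 41 or 59; 9.97 at 40 or 60).
- By true rate: the average exact half-width is 10 points or more only for p between 42.1% and 57.9%.
- If the true p is 50%, P(41 ≤ X ≤ 59) = 0.943.

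**Step 5. The two methods side by side, n = 100 (percentage points).**

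| Yes responses | Printed formula | Exact interval | Exact half-width |
|---|---|---|---|
| 50 | 9.80 | 39.83% to 60.17% | 10.17 |
| 60 | 9.60 | 49.72% to 69.67% | 9.97 |
| 80 | 7.84 | 70.82% to 87.33% | 8.26 |
| 90 | 5.88 | 82.38% to 95.10% | 6.36 |
| 95 | 4.27 | 88.72% to 98.36% | 4.82 |

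The gap at 50/100 is 10.17 − 9.80 = 0.37 points, more than the 10 − 9.80 = 0.20 points of room under the formula.

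**Step 6. Sensitivity.**
- Choice of exact method: inverting the exact binomial test gives a half-width of 10.04 points at 50/100, still not below 10.
- Number of eyes: the worst-case Clopper-Pearson half-width is 10.01 points at n = 103 and 9.97 at n = 104.

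**The case against.** The strongest reply has three parts.

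**The printed formula is computed correctly.** A closed-form approximation for planning, followed by an exact interval for reporting, is common practice. That is so, but the text does not call the formula an approximation, and it draws a strict inequality from it. A statement of approximately 10% would have been safe.

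**The primary analysis may include more than 100 eyes.** The questionnaire is completed after each surgery, and the full analysis set is all eyes with successfully completed surgery, with no follow-up requirement. Loss to follow-up after surgery therefore does not remove an eye from this analysis. If 120 subjects enrol and 10% fail screening, 120 × 0.90 = 108 have surgery, and the worst-case exact half-width is 9.78 points. This has force: the planned enrolment may well deliver the bound. It does not rescue the sentence as written, which is explicitly for 100 surgeries. Protocol section 8 also gives a target of 100 treated subjects, and surgeries not successfully completed would lower the count.

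**The discrepancy is negligible and the observed rate is unlikely to be near 50%.** Both parts are fair. If the true rate were 80% (an illustrative assumption), the chance of 41 to 59 yes responses would be about 1 in a million. The 94.3% in Step 4 applies only if the true rate is 50%. But 50% is the plan's own worst case, and the claim being checked is a worst-case bound. This argument limits the importance of the point without removing it.

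**Conclusion.** The concern holds. At n = 100 and p = 50%, the half-width of the planned interval is 10.17 points (10.12 on average), not below 10. The fault is a mismatch between the interval used to justify the sample size and the interval to be reported; the evaluation of the printed formula is correct.

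The result rests on 100 analysed surgeries, as the sentence states, and on reading exact as Clopper-Pearson. Test inversion reduces the excess from 0.17 to 0.04 points but does not remove it. With 104 or more analysed eyes the bound would hold.

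The consequence is minor. This is an optional correction that brings the stated figure into line with the planned analysis. It gives no reason to enlarge the study.

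**What to change.** In SAP section 7, Protocol 12.8 and the Protocol section 3 summary, replace the formula and the < 10% sentence with: *With 100 surgeries the half-width of the two-sided exact binomial 95% CI is at most 10.2 percentage points (50/100: 39.8% to 60.2%).* The remark that the half-width is widest at 50% can stay. Naming Clopper-Pearson as the exact method would settle which variant is meant.

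The cost is one sentence in three places, with no added enrolment and no change to any analysis. The stated figure becomes slightly less favourable. The two Protocol edits fall under Protocol section 4, which requires IRB/IEC approval, and health authority approval as applicable, before an amendment is implemented. Its exceptions are changes needed to mitigate immediate safety risks "or when the changes involve only logistical or administrative revisions". The sponsor would have to judge whether this edit counts as administrative; if not, it can wait for the next amendment.
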